### Appendix C: One Touch Stockings of Cambridge (OTS)

The participant is shown two displays with three colored balls presented as stacks suspended from a beam and a row of numbered boxes along the bottom of the screen.

[figure not shown]

In the first set of problems, the participant is asked to move the balls in the lower display to match that of the upper display.

Then, the participant is shown additional problems and asked to work out in her head how many moves are required to reach the solution.

### Appendix D: Hopkins Verbal Learning Test-Revised (HVLT-R)

[figure not shown]
| Word List                 | Learning Trials |         |         |         | Delayed Recall
Trial (20-25 min.) |
|---------------------------|-----------------|---------|---------|---------|--------------------------------------|
|                           | Trial 1         | Trial 2 | Trial 3 | Trial 4 |                                      |
| LION                      |                 |         |         |         |                                      |
| EMERALD                   |                 |         |         |         |                                      |
| HORSE                     |                 |         |         |         |                                      |
| TENT                      |                 |         |         |         |                                      |
| SAPPHIRE                  |                 |         |         |         |                                      |
| HOTEL                     |                 |         |         |         |                                      |
| CAVE                      |                 |         |         |         |                                      |
| OPAL                      |                 |         |         |         |                                      |
| TIGER                     |                 |         |         |         |                                      |
| PEARL                     |                 |         |         |         |                                      |
| COW                       |                 |         |         |         |                                      |
| HUT                       |                 |         |         |         |                                      |
| Total correct responses = |                 |         |         |         |                                      |

Completion Time      Start Time  
Trial 3 \_\_\_\_\_      Trial 4 \_\_\_\_\_

[figure not shown]
| Delayed Recognition Trial (Forced Choice) |     |           |     |               |     |              |     |
|---|-----|-----------|-----|---------------|-----|--------------|-----|
| 1. HORSE                                  | Y N | 7. house  | Y N | 13. HUT       | Y N | 19. TENT     | Y N |
| 2. ruby                                   | Y N | 8. OPAL   | Y N | 14. EMERALD   | Y N | 20. mountain | Y N |
| 3. CAVE                                   | Y N | 9. TIGER  | Y N | 15. SAPPHIRE  | Y N | 21. cat      | Y N |
| 4. balloon                                | Y N | 10. boat  | Y N | 16. dog       | Y N | 22. HOTEL    | Y N |
| 5. coffee                                 | Y N | 11. scarf | Y N | 17. apartment | Y N | 23. COW      | Y N |
| 6. LION                                   | Y N | 12. PEARL | Y N | 18. penny     | Y N | 24. diamond  | Y N |

### Appendix E: Trail Making Test (TMT)

#### Test Part A:

**Test Part B:**

## Appendix F: Patient Reported Outcomes Measurement Information System – Modified Cognitive Function

Please respond to each question or statement by marking one box per row.

[figure not shown]
In the past 7 days...

|   |  | Never | Rarely
(Once) | Sometimes
(Two or
three times) | Often
(About
once a day) | Very often
(Several
times a
day) |
|---|--|-------|------------------|--------------------------------------|--------------------------------|---|
| 1 | My thinking has been slow.....   | 5     | 4                | 3                                    | 2                              | 1   |
| 2 | It has seemed like my brain
was not working as well as
usual.....  | 5     | 4                | 3                                    | 2                              | 1   |
| 3 | I have had to work harder than
usual to keep track of what I
was doing.....  | 5     | 4                | 3                                    | 2                              | 1   |
| 4 | I have had trouble shifting back
and forth between different
activities that require thinking....  | 5     | 4                | 3                                    | 2                              | 1   |
| 5 | I have had trouble
concentrating .....  | 5     | 4                | 3                                    | 2                              | 1   |
| 6 | I have had to work really hard
to pay attention or I would
make a mistake .....  | 5     | 4                | 3                                    | 2                              | 1   |
| 7 | I have had trouble forming
thoughts .....   | 5     | 4                | 3                                    | 2                              | 1   |
| 8 | I have had trouble adding or
subtracting numbers in my
head.....   | 5     | 4                | 3                                    | 2                              | 1   |
| 9 | I have had trouble
remembering whether I did
things I was supposed to do,
like taking a medicine or
buying something I needed..... | 5     | 4                | 3                                    | 2                              | 1   |

**Before my cancer diagnosis...**

|    |   | Never | Rarely
(Once)                      | Sometimes
(Two or
three times) | Often
(About
once a day)   | Very often
(Several
times a
day) |
|----|---|-------|---------------------------------------|--------------------------------------|----------------------------------|---|
| 10 | I noticed problems with my thinking .....   | 5     | 4                                     | 3                                    | 2                                | 1   |
| 11 | I had trouble remembering whether I did things I was supposed to do, like taking a medicine or buying something I needed..... | 5     | 4                                     | 3                                    | 2                                | 1   |
| 12 | Compared to most other people my age with similar education, I was .....  |       |  Not as smart |  As smart    |  Smarter |   |

### Appendix G: Modified NASA Task Load Index (NASA-TLX)

|  |  |
|--|--|
| Mental Demand  | How mentally demanding was the task?                                   |
|    |  |
| Very Low   | Very High  |
| Performance  | How successful were you in accomplishing what you were asked to do?    |
|    |  |
| Perfect  | Failure  |
| Effort   | How hard did you have to work to accomplish your level of performance? |
|   |  |
| Very Low   | Very High  |
| Frustration  | How insecure, discouraged, irritated, stressed, and annoyed were you?  |
|  |  |
| Very Low   | Very High  |

## Appendix H: Wechsler Adult Test of Reading (WTAR)

|                  |                   |
|------------------|-------------------|
| 1. again         | 26. conscientious |
| 2. address       | 27. homily        |
| 3. cough         | 28. malady        |
| 4. preview       | 29. subtle        |
| 5. although      | 30. fecund        |
| 6. most          | 31. palatable     |
| 7. excitement    | 32. menagerie     |
| 8. know          | 33. obfuscate     |
| 9. plumb         | 34. liaison       |
| 10. decorate     | 35. exigency      |
| 11. fierce       | 36. xenophobia    |
| 12. knead        | 37. ogre          |
| 13. aisle        | 38. scurrilous    |
| 14. vengeance    | 39. ethereal      |
| 15. prestigious  | 40. paradigm      |
| 16. wreath       | 41. perspicuity   |
| 17. gnat         | 42. plethora      |
| 18. amphitheater | 43. lugubrious    |
| 19. lieu         | 44. treatise      |
| 20. grotesque    | 45. dilettante    |
| 21. iridescent   | 46. vertiginous   |
| 22. ballet       | 47. ubiquitous    |
| 23. equestrian   | 48. hyperbole     |
| 24. porpoise     | 49. insouciant    |
| 25. aesthetic    | 50. hegemony      |

### Appendix I: PROMIS-Depression

**Please respond to each question or statement by marking one box per row.**

**In the past 7 days...**

|   |  | Never | Rarely | Sometimes | Often | Always |
|---|--|-------|--------|-----------|-------|--------|
| 1 | I felt worthless.....                              | 1     | 2      | 3         | 4     | 5      |
| 2 | I felt helpless .....                              | 1     | 2      | 3         | 4     | 5      |
| 3 | I felt depressed .....                             | 1     | 2      | 3         | 4     | 5      |
| 4 | I felt hopeless .....                              | 1     | 2      | 3         | 4     | 5      |
| 5 | I felt like a failure.....                         | 1     | 2      | 3         | 4     | 5      |
| 6 | I felt unhappy .....                               | 1     | 2      | 3         | 4     | 5      |
| 7 | I felt that I had nothing to look forward to ..... | 1     | 2      | 3         | 4     | 5      |
| 8 | I felt that nothing could cheer me up.....         | 1     | 2      | 3         | 4     | 5      |

### Appendix J: PROMIS-Anxiety

**Please respond to each question or statement by marking one box per row.**

**In the past 7 days...**

|   |   | Never | Rarely | Sometimes | Often | Always |
|---|---|-------|--------|-----------|-------|--------|
| 1 | I felt fearful .....  | 1     | 2      | 3         | 4     | 5      |
| 2 | I found it hard to focus on anything other than my anxiety... | 1     | 2      | 3         | 4     | 5      |
| 3 | My worries overwhelmed me .....                               | 1     | 2      | 3         | 4     | 5      |
| 4 | I felt uneasy .....   | 1     | 2      | 3         | 4     | 5      |
| 5 | I felt nervous .....  | 1     | 2      | 3         | 4     | 5      |
| 6 | I felt like I needed help for my anxiety .....                | 1     | 2      | 3         | 4     | 5      |

## Appendix K: PROMIS-Sleep Disturbance

Please respond to each question or statement by marking one box per row.

**In the past 7 days...**

|   |                           | Very poor | Poor | Fair | Good | Very good |
|---|---------------------------|-----------|------|------|------|-----------|
| 1 | My sleep quality was..... | 5         | 4    | 3    | 2    | 1         |

**In the past 7 days...**

|   |   | Not at all | A little bit | Somewhat | Quite a bit | Very much |
|---|---|------------|--------------|----------|-------------|-----------|
| 2 | My sleep was refreshing .....                       | 5          | 4            | 3        | 2           | 1         |
| 3 | I had a problem with my sleep ....                  | 1          | 2            | 3        | 4           | 5         |
| 4 | I had difficulty falling asleep .....               | 1          | 2            | 3        | 4           | 5         |
| 5 | My sleep was restless.....                          | 1          | 2            | 3        | 4           | 5         |
| 6 | I tried hard to get to sleep.....                   | 1          | 2            | 3        | 4           | 5         |
| 7 | I worried about not being able to fall asleep ..... | 1          | 2            | 3        | 4           | 5         |
| 8 | I was satisfied with my sleep .....                 | 5          | 4            | 3        | 2           | 1         |

### Appendix L: Functional Assessment of Chronic Illness Therapy-Fatigue (FACIT-F)

Below is a list of statements that other people with your illness have said are important. **Please circle or mark one number per line to indicate your response as it applies to the past 7 days.**

|    |  | Not at all | A little bit | Some-what | Quite a bit | Very much |
|----|--|------------|--------------|-----------|-------------|-----------|
| 1  | I feel fatigued.....   | 0          | 1            | 2         | 3           | 4         |
| 2  | I feel weak all over .....   | 0          | 1            | 2         | 3           | 4         |
| 3  | I feel listless ("washed out").....                                    | 0          | 1            | 2         | 3           | 4         |
| 4  | I feel tired .....   | 0          | 1            | 2         | 3           | 4         |
| 5  | I have trouble starting things because I am tired .....         | 0          | 1            | 2         | 3           | 4         |
| 6  | I have trouble finishing things because I am tired.....         | 0          | 1            | 2         | 3           | 4         |
| 7  | I have energy .....  | 0          | 1            | 2         | 3           | 4         |
| 8  | I am able to do my usual activities.....                               | 0          | 1            | 2         | 3           | 4         |
| 9  | I need to sleep during the day.....                                    | 0          | 1            | 2         | 3           | 4         |
| 10 | I am too tired to eat.....   | 0          | 1            | 2         | 3           | 4         |
| 11 | I need help doing my usual activities .....                            | 0          | 1            | 2         | 3           | 4         |
| 12 | I am frustrated by being too tired to do the things I want to do ..... | 0          | 1            | 2         | 3           | 4         |
| 13 | I have to limit my social activity because I am tired.....             | 0          | 1            | 2         | 3           | 4         |

### Appendix M: Karnofsky Performance Status (KPS)

| Score | Criteria  |
|-------|---|
| 100   | Normal; no complaints; no symptom of disease.                               |
| 90    | Able to carry on normal activity; minor symptoms of disease.                |
| 80    | Normal activity with effort; some symptoms of disease.                      |
| 70    | Care for self. Unable to carry on normal activity or to do active work.     |
| 60    | Require occasional assistance, but able to care for most of personal needs. |
| 50    | Require considerable assistance for personal care.                          |
| 40    | Disabled; require special care and assistance.                              |
| 30    | Severely disabled; require continuous nursing care.                         |

### Appendix N: Functional Assessment of Cancer Therapy-General (FACT-G)

Below is a list of statements that other people with your illness have said are important. **Please circle or mark one number per line to indicate your response as it applies to the past 7 days.**

|   | PHYSICAL WELL-BEING   | Not at all | A little bit | Some-what | Quite a bit | Very much |
|---|---|-------------------|---------------------|------------------|--------------------|------------------|
| 1 | I have a lack of energy.....  | 0                 | 1                   | 2                | 3                  | 4                |
| 2 | I have nausea .....   | 0                 | 1                   | 2                | 3                  | 4                |
| 3 | Because of my physical condition, I have trouble meeting the needs of my family ..... | 0                 | 1                   | 2                | 3                  | 4                |
| 4 | I have pain .....   | 0                 | 1                   | 2                | 3                  | 4                |
| 5 | I am bothered by side effects of treatment .....                                      | 0                 | 1                   | 2                | 3                  | 4                |
| 6 | I feel ill .....  | 0                 | 1                   | 2                | 3                  | 4                |
| 7 | I am forced to spend time in bed .....  | 0                 | 1                   | 2                | 3                  | 4                |

|    | SOCIAL/FAMILY WELL-BEING  | Not at all | A little bit | Some-what | Quite a bit | Very much |
|----|---|-------------------|---------------------|------------------|--------------------|------------------|
| 8  | I feel close to my friends .....  | 0                 | 1                   | 2                | 3                  | 4                |
| 9  | I get emotional support from my family .....  | 0                 | 1                   | 2                | 3                  | 4                |
| 10 | I get support from my friends.....  | 0                 | 1                   | 2                | 3                  | 4                |
| 11 | My family has accepted my illness .....   | 0                 | 1                   | 2                | 3                  | 4                |
| 12 | I am satisfied with family communication about my illness.....  | 0                 | 1                   | 2                | 3                  | 4                |
| 13 | I feel close to my partner (or the person who is my main support).....  | 0                 | 1                   | 2                | 3                  | 4                |
|    | Regardless of your current level of sexual activity, please answer the following question. If you prefer not to answer it, please mark this box  and go to the next section. |                   |                     |                  |                    |                  |
| 14 | I am satisfied with my sex life.....  | 0                 | 1                   | 2                | 3                  | 4                |

|    | EMOTIONAL WELL-BEING                        | Not
at all | A little
bit | Some-
what | Quite
a bit | Very
much |
|----|---|-----------------------|-------------------------|-----------------------|------------------------|----------------------|
| 15 | I feel sad.....   | 0                     | 1                       | 2                     | 3                      | 4                    |
| 16 | I am satisfied with how I am coping with my illness ..... | 0                     | 1                       | 2                     | 3                      | 4                    |
| 17 | I am losing hope in the fight against my illness .....    | 0                     | 1                       | 2                     | 3                      | 4                    |
| 18 | I feel nervous .....                                      | 0                     | 1                       | 2                     | 3                      | 4                    |
| 19 | I worry about dying .....                                 | 0                     | 1                       | 2                     | 3                      | 4                    |
| 20 | I worry that my condition will get worse.....             | 0                     | 1                       | 2                     | 3                      | 4                    |

|    | FUNCTIONAL WELL-BEING                      | Not
at all | A little
bit | Some-
what | Quite
a bit | Very
much |
|----|--|-----------------------|-------------------------|-----------------------|------------------------|----------------------|
| 21 | I am able to work (include work at home).....            | 0                     | 1                       | 2                     | 3                      | 4                    |
| 22 | My work (include work at home) is fulfilling .....       | 0                     | 1                       | 2                     | 3                      | 4                    |
| 23 | I am able to enjoy life .....                            | 0                     | 1                       | 2                     | 3                      | 4                    |
| 24 | I have accepted my illness .....                         | 0                     | 1                       | 2                     | 3                      | 4                    |
| 25 | I am sleeping well .....                                 | 0                     | 1                       | 2                     | 3                      | 4                    |
| 26 | I am enjoying the things I usually do for fun.....       | 0                     | 1                       | 2                     | 3                      | 4                    |
| 27 | I am content with the quality of my life right now ..... | 0                     | 1                       | 2                     | 3                      | 4                    |

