## 1.0 BACKGROUND AND RATIONALE

### 1.1 Study Synopsis

This is a one-arm phase II interventional study in patients with breast cancer to investigate whether memantine can prevent cognitive decline during chemotherapy. We will recruit 56 participants with breast cancer referred to the UNC Breast Center, Hillsborough Oncology, or UNC REX Oncology clinics for initiation of adjuvant or neoadjuvant chemotherapy, perform a cognitive assessment at initiation (range: any time after establishing care to one week after first dose) and four weeks after completion of chemotherapy (range: two to twelve weeks after last dose), and treat with memantine 10 mg twice daily between the pre- and post-chemotherapy study assessments (estimated duration: 12-30 weeks). We will assess cognitive function objectively using a computerized cognitive assessment and a standard neuropsychological battery. To assess subjective cognitive function, we will use the Patient Reported Outcome Measurement Information System (PROMIS) Cognitive Function measure. Depression, anxiety, fatigue, menopausal status, and sleep are comorbidities known to affect cognitive function, and therefore will be assessed as covariates through self-report measures and, in the case of menopausal status, laboratory values. Depression, anxiety, health-related quality of life (HRQOL) and functional status will be evaluated as secondary outcomes. Cognitive and other secondary outcome measures will be repeated in a subset of participants who opt-in for longitudinal follow-up at 6 months (range: 4 to 8 months) post-chemotherapy. We will also assess the feasibility of our study by monitoring recruitment, retention, and adherence to memantine.

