### 1.2 Disease Background

Cancer-related cognitive impairment (CRCI) refers to a constellation of problems with memory, attention, and executive function that is associated with cancer and its treatments. There are over 16 million cancer survivors in the United States and an estimated 5.5 million suffer from CRCI. Specifically, up to 75% of patients with cancer report cognitive deficits during active treatment and up to 35% of survivors will demonstrate cognitive impairment on neuropsychological assessment (NPA) that can last years after treatment. CRCI can have profound consequences, including inability to return to work, reduced quality of life, and doubled risk of dementia. Given the substantial personal and societal burden of CRCI, and the absence of ways to prevent it, approaches that screen for CRCI and deliver effective interventions as soon after cancer diagnosis as possible are needed.

Most interventions for CRCI, including cognitive training and rehabilitation, physical activity, and meditation, however, are administered years after cancer treatment and have yielded inconsistent results. Perhaps the most essential study design issue impacting the efficacy of interventions is the timing of their

delivery relative to when cognitive issues are first appreciated. Specifically, because symptoms can persist for several years after cancer treatment and cognitive deficits are associated with underlying functional and structural brain changes, the extent to which CRCI is reversible is not clear. Another critical variable impacting reliable interpretation of intervention efficacy is lack of agreement about how to measure CRCI. Self-report instruments are criticized as potentially reflecting other comorbidities (e.g. depression, anxiety, fatigue), while other investigators raise concerns about the sensitivity and ecological validity of NPA. Further, despite International Cognition and Cancer Task Force (ICCTF) guidelines, neuropsychological batteries used in research remain highly heterogeneous.

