### 2.2 **Secondary Objectives**

**2.2.1** To compare pre- to post-chemotherapy changes in all other objective and self-reported cognitive function measures.

**2.2.2** To examine associations between objective and self-reported cognitive function with depression, anxiety, fatigue, menopausal status, baseline IQ, and perceived cognitive effort, cross-sectionally pre- and post-chemotherapy.

**2.2.3** To explore the impact of cognitive decline on health-related quality of life (HRQOL), functional status, depression, and anxiety.

**2.2.4** To estimate the feasibility of conducting a clinical trial of memantine for attenuating cognitive decline in patients with breast cancer during chemotherapy.

**2.2.5** To describe the safety of administering memantine to patients with breast cancer during chemotherapy.

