### 9.3 Data Analysis Plans

The primary outcome is change in the DMS score. A paired t-test will test if the change in DMS score from pre- to post-chemotherapy is statistically different from historical controls. Pre- to post-chemotherapy, as well as pre- to 6 months post-chemotherapy, changes in all other cognitive measures will also be evaluated using paired t-tests.

Linear regression models will be used to cross-sectionally evaluate associations between depression (PROMIS-D), anxiety (PROMIS-A), sleep (PROMIS-Sleep Disturbance), menopausal status, fatigue (FACIT-F), estimated pre-cancer IQ (WTAR), and cognitive effort (NASA-TLX) with both objective (DMS, HVLT-R, COWA, ANT, Digit Span) and self-reported (PROMIS) measures of cognitive function at baseline and post-chemotherapy. Linear mixed effects models will evaluate associations across pre- and post- time points.

Linear regression modeling will describe the associations between pre- to post-chemotherapy cognitive changes (DMS, HVLT-R, COWA, ANT, Digit Span, PROMIS) with post-chemotherapy depression and anxiety (PROMIS), HRQOL (FACT-G), and performance status (KPS).

Descriptive statistics will be used to estimate feasibility: 1.) recruitment rate (% of invited participants who enroll), 2.) attrition (% of enrolled participants who are not eligible for analysis of the primary outcome), and 3.) adherence to treatment (% self-reported doses of memantine taken).

We will tabulate all AEs, the dose at which they occurred, and if they led to dosing delays or removal from the study.

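### Section 9.3 does not carry fatigue or sleep into the objective 2.2.3 models, so an association between cognitive change and quality of life, function or mood may partly reflect fatigue

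*Combined protocol and SAP*

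**What the plan says.** Objective 2.2.3 reads: "To explore the impact of cognitive decline on health-related quality of life (HRQOL), functional status, depression, and anxiety". Its analysis is one sentence in section 9.3: "Linear regression modeling will describe the associations between pre- to post-chemotherapy cognitive changes (DMS, HVLT-R, COWA, ANT, Digit Span, PROMIS"), followed by "with post-chemotherapy depression and anxiety (PROMIS), HRQOL (FACT-G), and performance status (KPS"). No covariate is named, whether fatigue, sleep or the baseline value of the outcome.

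Section 1.1 states: "Depression, anxiety, fatigue, menopausal status, and sleep are comorbidities known to affect cognitive function, and therefore will be assessed as covariates". It does not say in which model. Section 1.2 adds a caution: "Self-report instruments are criticized as potentially reflecting other comorbidities (e.g. depression, anxiety, fatigue").

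In section 9.3, FACIT-F and PROMIS Sleep Disturbance appear only in the preceding paragraph. That paragraph serves objective 2.2.2 and relates them to cognitive function, first cross-sectionally and then in mixed models.

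Among the outcome forms, FACT-G (Appendix N) has "I have a lack of energy" as item 1 and "I am sleeping well" as item 25. The Time and Events Table (section 7.1) schedules FACIT-F, the sleep form and all four outcomes both before and after chemotherapy.

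**The concern.** A patient who becomes tired or sleeps badly during chemotherapy may report worse cognition, lower quality of life and poorer function at the same visit. A model with cognitive change as its only named predictor cannot separate that common cause from a link between cognition and the outcome. The plan accepts the premise, since it says that fatigue and sleep affect cognition, but leaves them out of the analysis meant to address impact.

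The risk looks greatest for PROMIS Cognitive Function, the one self-reported measure among the six predictors and the type of measure that section 1.2 cautions about. At stake is how a listed secondary objective is interpreted. The primary endpoint is not affected.

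**Working it through.** **1. Sample size.** The plan gives no figure for these models. The evaluable number, 45, comes from the primary calculation in section 9.2, which reproduces: d = 3/7.97 = 0.376, and a one-sample t-test at one-sided 0.05 with n = 45 has 79.98% power, against 80% stated.

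**2. Covariates, section by section.** Section 1.1 calls fatigue and sleep covariates. Section 5.8 places both forms under its covariates and secondary outcomes heading. Section 9.3 uses them for objective 2.2.2 and not for 2.2.3. So the commitment exists but is not carried through.

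**3. Shared content of the forms.**
- FACT-G: items 1 (energy) and 25 (sleep) are 2 of 27 items, or 8 of 108 raw points (7.4%). Item 7 (time in bed) is closely related; with it the count is 3 of 27, or 12 of 108 (11.1%).
- KPS: it has no energy or sleep item, but its levels are defined by normal activity and need for assistance. FACIT-F items 8 and 11 ask about the same things.
- PROMIS depression and anxiety: neither form has an energy or sleep item. For these the issue is ordinary confounding.

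**4. Size of an induced association.** Let C be cognitive change, F fatigue and Q the outcome, with C and Q unrelated given F. Then corr(C,Q) = corr(C,F) × corr(F,Q). At n = 45, two-sided p < 0.05 needs |r| = 0.294. The documents give neither correlation, so both are assumed: 0 to 0.5 for the first and 0.5 to 0.8 for the second. The two-sided 5% level is also an assumption, since the plan sets none for these models.

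Results from 20,000 simulated samples of 45 per setting; each range runs over corr(F,Q) from 0.5 to 0.8:

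| corr(C,F) | Induced r | p < 0.05 without F | p < 0.05 with F |
|---|---|---|---|
| 0 | 0 | about 5% | about 5% |
| 0.1 | 0.05–0.08 | 6–9% | about 5% |
| 0.2 | 0.10–0.16 | 10–18% | about 5% |
| 0.3 | 0.15–0.24 | 17–36% | about 5% |
| 0.4 | 0.20–0.32 | 26–59% | about 5% |
| 0.5 | 0.25–0.40 | 39–79% | about 5% |

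The last column assumes a single confounder measured without error. It shows the principle and does not predict how the adjusted model proposed below would perform.

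**The case against.** A reader might infer that fatigue will end up reported as the impact of cognitive decline. The documents do not support that. Section 9.3 undertakes only to describe associations, the objective is worded as exploratory, and no test or threshold is set for these models. Bias also needs fatigue to correlate with cognitive *change*, which the documents do not quantify; at zero correlation there is none. Five of the six predictors are objective tests, and the section 1.2 caution concerns self-report only.

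A reader might also infer that the outcome forms measure the same things as the fatigue and sleep forms. Clear energy and sleep overlap is limited to two FACT-G items. Because FACIT-F is not in the planned model, shared items alone do not bias it; they matter mainly once FACIT-F is added.

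Section 9.3 does not say that the models are univariable. It is silent, and sections 1.1 and 5.8 could be read as pointing towards adjustment.

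The strongest objection concerns mediation. If cognitive decline acted on quality of life entirely through fatigue, a linear model would show the same correlations as the confounding case, and the adjusted estimate would hide a real effect. For KPS, adjusting for FACIT-F also partly adjusts the outcome for itself.

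All of this stands as a limit on the claim and on the remedy. It does not close the gap: section 1.1 is not reflected in these models, the objective speaks of impact, and the planned estimate alone cannot show how far it depends on fatigue.

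**Conclusion.** The point holds as a gap in specification with a real but unquantified risk of confounding. Section 9.3 should be reconciled with section 1.1. An association found under objective 2.2.3 may partly reflect treatment fatigue, most plausibly when the predictor is PROMIS Cognitive Function.

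The tabulated rates illustrate the risk and do not estimate it. They rest on assumed correlations, 45 evaluable patients, a two-sided 5% test and no cognition–outcome link given fatigue. The documents do not show which row applies, or whether fatigue is a confounder, a mediator or both. They therefore do not support basing conclusions on the adjusted model alone.

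**What to change.** Amend section 9.3 for objective 2.2.3 as follows.

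- Keep each planned estimate. Beside it, report one adjusted for FACIT-F, PROMIS Sleep Disturbance and the baseline value of the outcome. State which time points of FACIT-F and sleep enter; because the predictor is a change score, using both is the natural choice.
- Interpret the two estimates together and describe the results as associations, not impact. Neither replaces the other.
- For FACT-G, repeat the adjusted model with items 1, 7 and 25 removed from the score.
- For KPS, note that FACIT-F items 8 and 11 share its content, so the adjusted estimate may be over-corrected.

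The cost is wording and computing time, with no new data and no patient burden. Six cognitive measures by four outcomes is 24 models if each measure gives one score. That means 24 adjusted fits, plus 6 repeats for FACT-G. The statistical price is a few degrees of freedom. Residual degrees of freedom fall from 43 (45 − 2) to 40 with one time point each for FACIT-F and sleep plus the baseline outcome (three added terms), or to 38 with both time points (five added terms). Over-adjustment remains possible if fatigue is a mediator, which is why both estimates are shown.
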